The phase IV DEFENDO Study involving OXERVATE™ 0.002% (20 mcg/mL) cenegermin-bk bj ophthalmic solution has since been undertaken to provide additional efficacy and safety information related to OXERVATE™ 0.002% (20 mcg/mL) cenegermin-bk bj ophthalmic solution. This study enrolled 37 Stage 1 NK patients who were treated with OXERVATE™ 0.002% (20 mcg/mL) cenegermin-bk bj ophthalmic solution 6 times per day at 2-hour intervals for eight weeks. The DEFENDO Study reported 33 probable and 20 possible adverse events (AEs) that were determined to be related to the Study Product; however, only 3 patients discontinued the study because of the AEs they experienced. While these data are still being analyzed, the DEFENDO Long-Term Follow-up Study is a continuation of the DEFENDO Study, which aims to understanding the efficacy and safety OXERVATE™.

0.002% (20 mcg/mL) cenegeamin-bk bj ophthalmic solution at 24 and 30 months after the completion of the DEFENDO Study.

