3.3 STUDY RATIONALE

This clinical study has been designed as a long-term follow-up study to the DEFENDO Study to understand the long-term clinical outcomes of OXERVATE™ 0.002% (20 mcg/mL) cenegeamin-bk bj ophthalmic solution in a group of Stage 1 NK patients who complete the DEFENDO Study. The primary objectives are to evaluate the long-term safety and efficacy (healing) of OXERVATE™ 0.002% (20 mcg/mL) cenegeamin-bk bj ophthalmic solution in Stage 1 NK patients who enrolled in the DEFENDO Study.

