5.1 INCLUSION CRITERIA

To be eligible for inclusion into this study, each patient must fulfil the following inclusion criteria:

1. Previously enrolled in the DEFENDO Study.
2. Satisfy all Informed Consent requirements.
 - The patient and/or his/her legal representative has read, signed, and dated the IRB approved Informed Consent document before any study-related procedures are performed.
3. Must have the ability and willingness to comply with study procedures.

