2.5 Analysis Population

The full analysis set (FAS) will include all enrolled patients who attended either 24-Month Study Visit, or 30-Month Study Visit, or both. The FAS will be used for both efficacy and safety analyses.

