2.10 Handling of Missing Data

The primary efficacy analysis will be based on observed cases (i.e. no missing data imputation).

All analyses unless specified will be conducted on an as observed case basis, that is, no further imputation of missing data will be carried out unless explicitly stated otherwise.

In the descriptive summaries, the number of subjects with missing data will be presented under the “Missing” category. Summary statistics for continuous variables will be calculated only on non-missing values. For categorical variables, missing values will be reported under the “Missing” category but not included in the denominator count when computing percentages. When continuous data will be summarized, only the non-missing values will be evaluated for computing summary statistics. Any exception will be declared.

Imputation for Missing Concomitant Medication and AE Start and Stop Days:

Missing and/or incomplete dates for concomitant medications and AEs will be imputed for calculating Start/Onset Day and Stop Day only. The Start/Onset Day and Stop Day may be used for calculating prior or concomitant medications or calculating treatment emergent AEs. Missing and/or incomplete dates will be imputed in a manner that assumes the worst case scenario (i.e. Start/Onset as close as possible to the First Study Treatment Administration and stopped such that it assumed to have lasted for the longest possible duration, taking into account that the Start/Onset date should not be after the Stop date).

Imputation for missing Stop Date:

- For a completely missing stop year (regardless of day or month) the medication/AE will be assumed to be ongoing.
- For a missing stop month (and a medication/AE that is not ‘Ongoing’) the medication/AE will be assumed to have ended the last available month of that year.
- For a missing stop day (and a medication/AE that is not ‘Ongoing’) the medication/AE will be assumed to have ended on the last day of the month if the month is available.

Imputation for missing Start/Onset Date:

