5 ANALYSIS OF EFFICACY

All efficacy analyses will be considered exploratory and performed based on the observed cases in the FAS population. No missing data imputation will be considered.

For continuous efficacy endpoints, descriptive statistics of the observed and change from baseline will be tabulated by visit where that endpoint is assessed. Where appropriate, the asymptotic 95% confidence intervals of mean change from baseline will be presented as well as p values from one-sample t-test and Wilcoxon signed rank test (depending on the distribution of the data) to compare the observed values vs baseline.

For responder/categorical efficacy endpoints, analyses will include percentage of responders/categorized results, and associated exact (Clopper-Pearson) 95% confidence intervals where appropriate as well as p values from a binomial test to assess that responder rates are greater than zero.

- Percentage of patients who had corneal epithelial healing at Week 8 in the DEFENDO Study, who maintain healing at Month 24 and Month 30 of the long-term follow-up

The patients who had corneal epithelial healing at Week 8 and maintain healing at Month 24 and Month 30 will be summarized as a binary goal attainment variable (Yes/No) based on the subset of patients who achieved corneal epithelial healing at Week 8, as determined by the CRC.

- Percentage of patients who did not have corneal epithelial healing at Week 8 in the DEFENDO Study who have a healed corneal epithelium at Month 24 and Month 30 of the long-term follow-up

The patients who did not have corneal epithelial healing at Week 8 and who have corneal epithelial healing at Month 24 and Month 30 will be summarized as a binary goal attainment variable (Yes/No) based on the subset of patients who did not have corneal epithelial healing at Week 8, as determined by the CRC.

- Percentage of patients who achieved an improvement in corneal sensitivity at Week 8 in the DEFENDO Study who still have improvement in corneal sensitivity at Month 24 and Month 30 of the long-term follow-up

The improvement in corneal sensitivity is defined as change from baseline > 0 (cm) of the study eye. The patients who achieved an improvement in corneal sensitivity at Week 8 and still have improvement in corneal sensitivity at Month 24 and Month 30 will be summarized as a binary goal attainment variable (Yes/No) based on the subset of patients who achieved an improvement in corneal sensitivity at Week 8.

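### A full-analysis-set patient with no Week 8 reading-center grade is counted in no planned healing percentage, and no visible table gives the protocol's overall healing rate at Months 24 and 30

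*SAP*

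**What the plan says.** **Healing subsets.** SAP section 5 describes two healing analyses, shown as Tables 14.2.1.1 and 14.2.1.2 in SAP Appendix 2. The first is "based on the subset of patients who achieved corneal epithelial healing at Week 8, as determined by the CRC". The second is "based on the subset of patients who did not have corneal epithelial healing at Week 8, as determined by the CRC". CRC is the Central Reading Center.

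**Missing data.** Section 5 works on observed cases and states: "No missing data imputation will be considered". SAP 2.10 adds that for categorical variables "missing values will be reported under the “Missing” category but not included in the denominator count when computing percentages".

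**Who can be in the analysis.** The entry criterion in Protocol 5.1 is "Previously enrolled in the DEFENDO Study"; finishing DEFENDO is not required. SAP 2.5 defines the full analysis set (FAS) as "all enrolled patients who attended either 24-Month Study Visit, or 30-Month Study Visit, or both". The primary objective (SAP 1.1; Protocol 4.1) is stated for Stage 1 patients who enrolled in DEFENDO.

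**Overall endpoint.** Protocol 8.1 and the synopsis first list the percentage healed at 24 and 30 months, with no condition on Week 8. The two Week 8 subsets are sub-items of it. SAP section 9 plans no changes from the protocol.

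**Early leavers.** Protocol 3.2 reports that in DEFENDO "only 3 patients discontinued the study because of the AEs they experienced".

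**The concern.** Two subsets defined by the presence and by the absence of healing look as if they partition the analysis set. They do so only if every FAS patient has a Week 8 grade, and nothing in the plan ensures that. A patient may lack one because of leaving DEFENDO before Week 8, missing that visit, or having an image that could not be graded. Under the observed-case rule such a patient belongs to neither subset.

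Healing is the efficacy part of the primary objective, and descriptive percentages are all this study will produce. If the only healing percentages are conditional on a Week 8 grade, the reported population is narrower than the one in the objective, and the shortfall is not shown as a line in any table. The not-healed subset is also likely to be small, so where a few ungraded patients are placed can move its percentage a good deal.

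**Working it through.** The plan states no power or precision figure on this point, so there is nothing to reproduce. The check compares the texts and then works out a range.

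**Step 1. Follow a patient with no Week 8 grade.**
- Eligible? Yes: enrollment in DEFENDO suffices (Protocol 5.1).
- In the FAS? Yes, with a Month 24 or Month 30 visit (SAP 2.5).
- In Table 14.2.1.1? No: it needs a grade of healed at Week 8.
- In Table 14.2.1.2? Not under observed cases: it needs a grade of not healed.
- In an overall healing table? None is visible. Appendix 2 goes from 14.2.1.1 and 14.2.1.2 straight to 14.2.2.1, with no redaction mark between them.
- In Listing 16.2.6.1 (staining and healing)? Yes, but a listing gives no percentage.

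The *Missing* category of SAP 2.10 does not clearly help. It shows a missing outcome inside a table, whereas here the value that defines membership of the table is missing.

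**Step 2. Share left out.** Share = m/N, where m is the number of FAS patients without a Week 8 grade and N is the FAS size. Neither is given. The maximum N is 37 (SAP section 7); N = 20 to 37 and m = 1 to 5 are assumptions.
- m = 3: 3/37 = 8.1%, 3/30 = 10.0%, 3/25 = 12.0%, 3/20 = 15.0%.
- Full assumed range: 1/37 = 2.7% to 5/20 = 25.0%.
- m = 0: 0%.

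**Step 3. Effect on healing overall (assumed counts).** Take N = 30 with 20 healed, 7 not healed and 3 ungraded at Week 8. At Month 24, 18 of the 20 and 3 of the 7 are healed.
- The two planned tables put together: (18 + 3)/27 = 77.8%.
- All 30, if none of the 3 is healed: 21/30 = 70.0%.
- All 30, if all 3 are healed: 24/30 = 80.0%.

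**Step 4. Effect on the not-healed table (assumed counts).** Take N = 37 and m = 3, leaving 34 graded. A 72% Week 8 healing rate, borrowed from the first approval study in Protocol 3.2 for illustration only, gives 0.72 × 34 = 24.5, taken as 24 healed and 10 not healed. Suppose 5 of the 10 heal later. Intervals are exact (Clopper-Pearson) 95%.
- As planned: 5/10 = 50.0% (18.7 to 81.3).
- Ungraded counted as not healed at Week 8, none healed later: 5/13 = 38.5% (13.9 to 68.4).
- The same, all three healed later: 8/13 = 61.5% (31.6 to 86.1).

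With m = 3, the not-healed subset runs from about 3 patients (N = 25, assumed rate 85%: 22 graded, 19 healed) to about 12 (N = 37, the US trial's 65.2%: 34 graded, 22 healed).

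**Step 5. Corneal sensitivity.** Tables 14.2.2.2 and 14.2.2.3 have the same structure and the same gap. The gap matters less there, because Table 14.2.2.1 reports change from baseline without conditioning on Week 8 and so keeps these patients.

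**The case against.** A reader might infer that the three patients who stopped DEFENDO for adverse events are the ones left out, and that this flatters the product. The documents do not support either step.

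- **Timing and rollover are unknown.** DEFENDO had 8 weeks of treatment and then 6 months off treatment (Protocol 4.3). A patient who left in the second period may already have a Week 8 grade. Patients lost to follow-up are not eligible (Protocol 4.3 and 5), and the rationale in Protocol 3.3 even describes the study as being "in a group of Stage 1 NK patients who complete the DEFENDO Study", although the inclusion criterion does not say so.
- **Visit mapping may fill the gap.** SAP 2.4 assigns data to the nearest scheduled visit. This stands in part. Treatment visits are Weeks 2, 4 and 8 (SAP 2.2), so an exit visit after the midpoint of Weeks 4 and 8, (4 + 8)/2 = Week 6, could count as Week 8. An earlier exit could not, and a gradable image is still needed.
- **Direction.** Step 3 moves down or up depending on three unknown outcomes. Standard of care, including the commercial product, is permitted during follow-up (Protocol 6.2), so those outcomes cannot be presumed.
- **The wording could be read loosely.** Not having healed at Week 8 might include patients with no documented healing. The references to CRC determination and observed cases favor the narrower reading, but the text does not settle it. Two programmers could therefore produce different denominators.
- **Denominators are reported.** SAP 2.8 requires the number with available data, so the subset sizes will show. A careful reader could subtract them from the FAS, but could not tell a missing Week 8 grade from a missing later one.
- **Table 14.2.1.1 is right to exclude these patients.** Maintained healing presupposes healing at Week 8. The gap lies in the second table and in the absence of an overall one.

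All analyses are exploratory (SAP 2.9). That removes any question of error control, but not the need to define a denominator.

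**Conclusion.** The point holds as a gap in the definition of the healing analysis. Under the stated rules, an FAS patient without a Week 8 CRC grade contributes to no healing percentage, and the protocol's overall healing endpoint has no visible analysis. Part of the SAP's efficacy text and table list is redacted, so the absence of an overall table is established for the visible text only; the unbroken table numbering makes a hidden one unlikely.

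The size is unknown and may be nil. It is 8.1% to 15.0% of patients if all three adverse-event discontinuations lacked a grade and rolled over, with 37 down to 20 rollovers assumed. The plan cannot be said to favor the product, nor to exclude those three patients in particular. The change is still worth making, because it decides which patients count in the efficacy part of the primary objective.

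**What to change.** 1. Add the protocol's overall endpoint: percentage healed at Month 24 and at Month 30 among all FAS patients with a CRC grade at that visit, with an exact 95% confidence interval.
2. Present healing as one table per visit. Rows: Week 8 healed, Week 8 not healed, no Week 8 grade. Columns: healed, not healed, missing. Totals equal the FAS. The two planned conditional percentages are read from the first two rows. Counts suffice in the third row if it holds only a few patients.
3. State in SAP section 5 how a missing Week 8 grade is handled, and report how many patients lack one after the visit mapping of SAP 2.4.
4. As a sensitivity analysis, count patients without a Week 8 grade with those not healed at Week 8. It should stay secondary, since it mixes graded non-healers with patients whose Week 8 status is unknown.
5. Add a *no Week 8 value* row to the corneal-sensitivity responder tables (14.2.2.2 and 14.2.2.3).

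The cost is a few lines of SAP text and changed table shells, with no new data. If every FAS patient has a Week 8 grade, the extra row shows zero and nothing is lost.

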7. **EQ-5D-5L:** This self-administered questionnaire will be completed by the patient before any ophthalmic examination is performed at a given study visit. The EQ-5D is a standardized measure of health status developed by the EuroQol Group to provide a simple, generic measure of health for clinical and economic appraisal.
8. **Ophthalmic Examinations:** The following examination/procedures will be performed on BOTH EYES and in the below order. Grading scales and a detailed description of the examinations/procedures are described in the MOP:
 - a. **Best-Corrected Distance Visual Acuity (BCDVA):** Vision will be measured using an Early Treatment Diabetic Retinopathy Study (ETDRS) visual acuity chart at 4 meters (13 feet) and recorded in Logarithm of the Minimum Angle of Resolution (LogMAR). BCDVA testing should precede the administration of any eye drops to dilate or anesthetize the eye, or any examination requiring contact with the eye. If vision is corrected, the same correction should be used throughout the BCDVA testing.
 - b. **External Ocular Examination:** The motility of the extraocular muscles and the appearance and function of the eyelids will be evaluated before the instillation of any dilating or anesthetic eye drops.
 - c. **Slit-Lamp Examination (SLE):** A SLE will be used to assess eyelids, lashes, conjunctiva, cornea, lens, iris, and anterior chamber. The SLE must be performed before the instillation of any dilating or anesthetic eye drops or the fluorescein agent.
 - d. **Corneal Photo without Fluorescein:** Photos of the cornea of both eyes will be taken after the SLE and before the instillation of fluorescein agent by a slit-lamp camera using white, diffuse (homogenous) frontal illumination.
 - e. **Instill Fluorescein**
 - f. **Tear Film Break-Up Time (TFBUT)**

- g. **Corneal Photography with Fluorescein:** A corneal photo of both eyes using cobalt blue illumination will be taken to document the observed corneal findings.
- h. **Corneal Sensitivity:** Corneal Sensitivity will be measured using a Cochet Bonnet aesthesiometer before the instillation of any dilating or anesthetic eye drops. Corneal sensitivity will be assessed in one quadrant of each eye.
- i. **Schirmer Test without Anesthesia (Schirmer I)**

- C CCI [REDACTED]
- C CCI [REDACTED]

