8 ENDPOINTS

8.1 STUDY ENDPOINTS

- Percentage of patients who have corneal epithelial healing at 24 months and 30 months of the long-term follow-up.
 - Percentage of patients who had corneal epithelial healing at week-8 in the DEFENDO Study, who maintain healing at month 24 and month 30 of the long-term follow-up.
 - Percentage of patients who did not have corneal epithelial healing at week-8 in the DEFENDO Study who have a healed corneal epithelium at month 24 and month 30 of the long-term follow-up.
- Percentage of patients who achieved an improvement in corneal sensitivity at 24 months and 30 months of the long-term follow-up.
 - Percentage of patients who achieved an improvement in corneal sensitivity at week-8 in the DEFENDO Study who still have improvement in corneal sensitivity at 24 months and 30 months of the long-term follow-up.
 - Percentage of patients who did not achieve an improvement in corneal sensitivity in the DEFENDO Study who have improvement in corneal sensitivity at 24 months and 30 months of the long-term follow-up.
- Change from the Baseline Visit in the DEFENDO Study in Schirmer I scores at 24 months and 30 months of the long-term follow-up.
- Change from the Baseline Visit in the DEFENDO Study in TFBUT at 24 months and 30 months of the long-term follow-up.
- Change from the Baseline Visit in the DEFENDO Study in BCDVA at 24 months and 30 months of the long-term follow-up.
- Percentage of patients who achieved a 15-letter improvement in BCDVA at 24 months and 30 months compared to the Baseline Visit and Week 8 of the DEFENDO Study.
- Change from the Baseline Visit in the DEFENDO Study in quality of life as measured with the IDEEL at 24 months and 30 months of the long-term follow-up.
- Change from the Baseline Visit in the DEFENDO Study in quality of life as measured with the EQ-5D-5L at 24 months and 30 months of the long-term follow-up.

CCI

CCI

CCI

CCI

CCI

[figure not shown]
CCI

CCI

CCI

CCI

C

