1.3.3.3 Best Corrected Distance Visual Acuity (BCDVA)

The logarithm of the minimal angle of resolution (logMAR) visual acuity score (ranged from -0.3 to 1) will be recorded at Month 24 and 30.

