2.8 Descriptive Summaries

Summary statistics and statistical analyses will be performed only for subjects included in the relevant analysis population. For the calculation of summary statistics and statistical analysis, unrounded data will be used. For endpoints that are continuous in nature: number of observations, mean, median, 25th and 75th quartiles, minimum and maximum, and standard deviation (SD) values will be presented as descriptive statistics summary for both observed values and change from baseline values at each scheduled visit if applicable. For endpoints that are categorical in nature: frequency counts and percentages will be presented as descriptive statistics summary at each scheduled visit if applicable. The number of subjects / eyes with available data (n) will also be reported.

The number of decimal places to display for calculated data will be determined by the original scale of the data. Means and medians will be reported with one (1) additional decimal place. Standard deviation will be reported with two (2) additional decimal places. Minimum and maximum will be reported with the same number of significant digits as the method of capture.

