- Percentage of patients who did not achieve an improvement in corneal sensitivity at Week 8 in the DEFENDO Study who have improvement in corneal sensitivity at Month 24 and Month 30 of the long-term follow-up

The patients who did not achieve an improvement in corneal sensitivity at Week 8 and who have improvement in corneal sensitivity at Month 24 and Month 30 will be summarized as a binary goal attainment variable (Yes/No) based on the subset of patients who did not achieve an improvement in corneal sensitivity at Week 8.

- Mean change in corneal sensitivity from baseline and Week 8 at Month 24 and Month 30

The corneal sensitivity (cm) in the NEI zone of the study eye as measured by the Cochet-Bonnet aesthesiometer will be summarized as a continuous variable.

- Schirmer I change from baseline and Week 8 to Month 24 and Month 30

The Schirmer tear test result (mm) in the study eye will be summarized as a continuous variable.

- TFBUT change from baseline and Week 8 to Month 24 and Month 30

The average TFBUT result (sec) of two repeat measurements in the study eye will be summarized as a continuous variable.

- Mean change in BCDVA from baseline and Week 8 to Month 24 and Month 30

The logMAR visual acuity score in the study eye will be summarized as a continuous variable.

- Percentage of patients that achieve a 15-letter gain from baseline and Week 8 in BCDVA at Month 24 and Month 30

The patients that achieve a 15-letter gain in BCDVA will be determined based on $\text{logMAR} - \text{Baseline logMAR} \leq -0.3$. It will be analyzed using a binary goal attainment variable (Yes/No).

- IDEEL change from baseline and Week 8 at Month 24 and Month 30

Subscores will be derived for the following modules and will be calculated only if at least 50% of the items of the dimension are completed; otherwise, the scores are missing.

Module 1:

Dry eye impact on daily life (27 questions) comprising 3 QoL domains: 1.a “Daily activities limitations”, 1.b “Emotional wellbeing” and 1.c “Work limitations”. 26 questions will be considered as part of one of these 3 domains. Question 22 will not be considered part of a domain.

1.a: Daily Activities

Daily activities section	Used in calculation of domain score?
1. Doing close work in the morning or afternoon (such as crossword puzzles, reading, looking at a computer, and/or sewing)	Yes
2. Doing close work in the evening or at night	Yes
3. Driving	Yes

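### The 15-letter BCDVA rule can score an exact 15-letter gain as a failure on unrounded data, and the plan does not show how many study eyes have no room to gain 15 letters

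*SAP*

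**What the plan says.** The endpoint in Protocol 8.1 is "Percentage of patients who achieved a 15-letter improvement in BCDVA at 24 months and 30 months compared to the Baseline Visit and Week 8", where both reference visits are those of the parent study. SAP section 5 repeats it as "Percentage of patients that achieve a 15-letter gain from baseline and Week 8 in BCDVA at Month 24 and Month 30". The sentence that defines the responder in that section begins "The patients that achieve a 15-letter gain in BCDVA will be determined based on" and ends in a single formula, which subtracts Baseline logMAR and calls the patient a responder if the result is -0.3 or lower. Appendix 2 of the SAP lists two tables: 14.2.5.2 (gain from baseline) and 14.2.5.3 (gain from Week 8).

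Three other statements bear on how the rule works:

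- **Scale.** SAP 1.3.3.3 describes the logMAR "visual acuity score (ranged from -0.3 to 1) will be recorded at Month 24 and 30". Lower is better, so -0.3 is the best recordable score.
- **Rounding.** SAP 2.8: "For the calculation of summary statistics and statistical analysis, unrounded data will be used".
- **Denominator.** SAP 5: "All efficacy analyses will be considered exploratory and performed based on the observed cases in the FAS population". The unit is the study eye (SAP 2.6), no subgroups are planned (SAP 2.7), and the protocol's eligibility criteria (5.1 and 5.2) do not mention acuity.

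**The concern.** A responder rule should give *Yes* to every patient who meets the definition, and a reader should be able to tell what a low rate means. This rule can fall short on both counts.

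The cut-off sits exactly on the value that a 15-letter gain produces. Most two-decimal logMAR values have no exact binary form, so a difference that is -0.30 on paper may be stored as slightly more than -0.3. A program that follows the SAP literally then records *No*. In a study of at most 37 patients, one such case is visible in the reported percentage.

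The cut-off is also as large as the whole distance from 0.00 to the best score on the scale. An eye that starts better than 0.00 is a certain non-responder but is counted in the denominator. Neither responder table is planned to show how many such eyes there are. Part of a low rate could then be read as absence of visual benefit when those eyes had no room to gain 15 letters. The baseline and Week 8 tables may also have different attainable maxima.

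**Working it through.** The plan gives no expected rate, power or sample-size figure for this endpoint, so there is no figure of that kind to reproduce. The cut-off itself is consistent with 15 letters at 0.3 / 15 = 0.02 logMAR per letter.

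**Inputs**

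- Cut-off of -0.3: SAP 5.
- Score range -0.3 to 1 at Months 24 and 30: SAP 1.3.3.3. I assume that reference values lie in the same range.
- Unrounded data: SAP 2.8.
- Maximum n = 37: SAP 7.
- Assumed, not in the documents: recording in 0.02 steps, the number of eyes better than 0.00, and the response rate.

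**1. Boundary comparison**

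Take reference values r = 0.00, 0.02, ..., 1.00, which is 51 values. For each, set the follow-up value to r - 0.30 (an exact 15-letter gain), compute follow-up minus reference in double precision, and test whether it is ≤ -0.3.

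- Example: 0.40 - 0.70 evaluates to -0.29999999999999993, which is greater than -0.3, so the result is *No*.
- Failures: r = 0.58, 0.70, 0.82, 0.84, 0.86, 0.94, 0.96 and 0.98, that is 8 of 51.
- On a coarser grid of 0.1 steps (11 references from 0.0 to 1.0), only 0.70 fails, 1 of 11.
- The error goes one way. No 14-letter gain (0.28) on the 0.02 grid passes the rule.
- With the difference rounded to 0.01 first, none of the 51 fails.
- Weight of one misclassified patient: 1/37 = 2.7 percentage points.

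The 8 of 51 is a share of possible starting values, not of patients. A patient is affected only if the gain is exactly 15 letters from one of those values.

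**2. Ceiling**

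For reference r, the best attainable change is -0.3 - r. This is ≤ -0.3 only if r ≥ 0.00. At r = 0.00 the eye must reach the best score on the scale. At r = -0.02 it would need -0.32, which the scale does not have.

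Let f be the share of study eyes with r < 0.00. Those eyes contribute no responders, so

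rate in all eyes = rate in eyes able to respond × (1 - f).

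Illustration with n = 37 and a rate of about 20% among eyes able to respond (responders rounded to whole patients, Clopper-Pearson 95% intervals):

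| Eyes better than 0.00 | f | All eyes | Eyes at 0.00 or worse |
|---|---|---|---|
| 0 | 0% | 7/37 = 18.9% (8.0 to 35.2) | 7/37 = 18.9% (8.0 to 35.2) |
| 4 | 11% | 7/37 = 18.9% (8.0 to 35.2) | 7/33 = 21.2% (9.0 to 38.9) |
| 7 | 19% | 6/37 = 16.2% (6.2 to 32.0) | 6/30 = 20.0% (7.7 to 38.6) |
| 11 | 30% | 5/37 = 13.5% (4.5 to 28.8) | 5/26 = 19.2% (6.6 to 39.4) |
| 19 | 51% | 4/37 = 10.8% (3.0 to 25.4) | 4/18 = 22.2% (6.4 to 47.6) |

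The first row matters as much as the last: if no study eye is better than 0.00, nothing changes.

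**The case against.** A reader might infer from the ceiling that the reported rate is biased downwards. The documents do not support that. The protocol's endpoint is a percentage of patients, with no restriction to eyes that have room to improve, and the SAP estimates that quantity as defined. A patient who starts at -0.1 and ends at -0.3 did not gain 15 letters. This objection stands in full.

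A reader might also infer that good starting acuity is likely because the disease is Stage 1, or that the Week 8 table is hit harder because treated eyes have improved. Neither is shown. Protocol section 3 describes Stage 1 by corneal findings and reduced sensation, not by acuity, and says that the epitheliopathy can lead to visual impairment. Improvement by Week 8 removes room only for eyes that cross below 0.00: an eye that goes from 0.8 to 0.4 can still gain 15 letters. No acuity distribution is given for either visit.

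The planned outputs also soften the problem. Mean logMAR change from both references is analysed (Table 14.2.5.1), SAP 2.8 adds quartiles and extremes, and Listing 16.2.6.3 gives BCDVA by patient, so the eyes concerned could be counted by hand. All efficacy analyses are exploratory. What remains is that the responder tables do not show the count, and the mean change has the same ceiling.

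The formula's silence on Week 8 is a wording gap only, because the endpoint heading and the title of Table 14.2.5.3 make the reference clear.

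On rounding, the failures all lie at 0.58 or worse and need an exact 15-letter gain, so few patients, perhaps none, would be affected. That limits the size but does not make the literal rule correct.

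**Conclusion.** The point holds in a limited form.

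- **Boundary.** Followed literally on unrounded data, the rule can misclassify a true 15-letter gain. With 0.02 steps, 8 of 51 exact gains fail, at about 2.7 points per affected patient if n = 37 (more if fewer patients roll over). The number affected cannot be known from the documents. The result rests on the assumed step size and on ordinary double-precision arithmetic.
- **Ceiling.** A study eye better than 0.00 at the reference visit cannot respond. Relative to eyes able to respond, the all-patient rate is reduced by exactly the fraction f, which is unknown and may be zero. This affects how a low rate is read. It does not make the protocol's endpoint wrong.

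Neither fault threatens the study's conclusions as a whole, but both can be removed cheaply.

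**What to change.** In SAP section 5, write the rule as ROUND(logMAR - reference logMAR, 0.01) ≤ -0.30, with reference = Baseline for Table 14.2.5.2 and Week 8 for Table 14.2.5.3. State that this rounding is an exception to SAP 2.8.

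In both tables, keep the observed-case rate in the full analysis set as the main row. Add the number of study eyes with reference logMAR below 0.00, and a supplementary rate with its exact interval among study eyes at 0.00 or worse. SAP 5 already uses denominators restricted by earlier status for healing and corneal sensitivity, so the format is familiar. SAP 2.7 should mention the added row.

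**Cost.** A few lines of SAP text, one line of code and two extra rows in each of two tables, with no new data. The supplementary rate has a smaller denominator and usually a wider interval: with 11 such eyes in the illustration, 6.6 to 39.4% against 4.5 to 28.8%. The Week 8 version also selects on a post-treatment value, so regression to the mean may raise it. It should be labelled descriptive and should not replace the main row.
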